## 7.3 Center Pooling

CIP342 LENNY Statistical Analysis Plan	Form
Revision 2.0 Page 16 of 31	Medtronic

The study is expected to be conducted in four countries. The same clinical investigational plan and training is followed, and standardized data collection methodology and electronic case report forms (eCRF) are used in all sites.

A descriptive summary of both study phase and continuation phase primary endpoints will be reported by country.

# 7.4 Handling of Missing, Unused, and Spurious Data and Dropouts

The Primary endpoints analyses are based on ITT using a random effect model that uses available data and accounts for missing at random. In addition, sensitivity analyses will be performed on PP set.

For per protocol analysis, if A1c is collected out of window (± 14 days from target visit date) A1c will be considered missing for that particular period/visit.

For the Run-in period, glycemic variability metrics from device data will be derived if a minimum number of 2880 of SG values (288 SG values/day × 10 days out of 14 days) is available, otherwise that data will be considered as missing.

In the case of dates collected at baseline with missing day and/or month the next procedure will be applied. A missing day and month will be imputed using the month 'July 1' and a missing day will be imputed with the day '15'. This applies only to dates related to medical history and baseline information with missing month and/or day.

For tables and listings of safety data a conservative/worst case scenario approach will be taken in case of partially missing dates. For the date of discharge with missing day, the day will be set to last day of that month. For the date of admission with missing day, the day will be set to first day of that month. If that is before the start of the study phase (within the same month), then the day will be set equal to today of the start of the study phase. Otherwise, if it is before the day of the start of the run-in (within the same month), then it will be set today of the start of

Outliers and influential observations will be identified via graphical plots. Once outliers or influential observations are identified, the study team will be informed and according to their decision the analysis for primary endpoint may be repeated using a statistical method robust against outliers. Additional exploratory analyses will be conducted as deemed appropriate.

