4.4 Safety Endpoints

The following safety endpoints will be assessed for each treatment during each period in the study phase and continuation phase:

- Number of severe hypoglycemic events
- Number of Diabetic Ketoacidosis events (DKA)
- Number of Serious Adverse Events (SAEs)
- Number of Serious Adverse Device Events (SADEs)
- Number of Unanticipated Serious Adverse Device Events (USADEs)

-		

5 Study Design

This study is a pre-market, prospective, open-label, multi-center, randomized crossover trial in paediatric subjects (2-6 years old) with type 1 diabetes. The study consists of a run-in phase, a study phase and a continuation phase (see **Figure 3** for an overview).

Run-in Phase (Visit 2-3):

The purpose of the run-in phase (2 to 4 weeks) is to train subject's parent(s)/legal guardian(s) on the MiniMed 780G system in Manual Mode with Suspend before low activated and to collect 2 weeks of baseline data. At the end of Run-in Phase, subjects will be randomized into 2 sequences (A and B).

D00674412

Successful completion of run-in phase requires sensor usage \geq 70% over the previous 2 weeks during the run-in phase. If this is not achieved (e.g. sensor felt off) the run-in phase can be extended for another 7 to 14 days to achieve sensor usage \geq 70%.

Study Phase (Visit 3A-11):

During the study phase, each sequence consists of 2 phases of 12 weeks each separated by a 2-week washout phase for a total of 26 weeks.

- Sequence A: subjects will start using the MiniMed 780G system in Auto Mode for 12 weeks (Treatment). The washout phase of 2 weeks will be followed by a 12-week phase where subjects will use 780G system in Manual Mode with SBL activated (Control).
- Sequence B: subjects will continue to use MiniMed 780G system in Manual Mode with SBL activated for 12 weeks (Control). After a washout phase of 2 weeks, subjects will start to use the MiniMed 780G system in Auto Mode for a 12-week phase (Treatment).

During washout period all the subjects will use MiniMed 780G system in Manual Mode with SBL activated.

Continuation Phase (Visit 12-15):

The continuation phase consists of 2 periods.

Enrolled subjects will enter the continuation phase period 1 and will use MiniMed 780G system in Auto Mode for 18 weeks +/- 6 weeks. At the end of the continuation phase period 1, subjects will be randomized into 2 arms (A2 and B2).

- Arm A2: Subjects will start using the MiniMed 780G BLE 2.0 system with the DS5 sensor for 12 weeks

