 - Review adverse events or device deficiencies, if any.

Sequence A and B:

- Visit 4 (Office/Remote): Follow up visit [Visit 3+14 days (Window ± 5 days)]
 - Ensure CareLink upload was done
 - \circ Collection of sensor site location
 - Review Pump therapy/adjust settings (see **Table 6**).
 - Retrain subject on 780G system as needed.
 - Review adverse events or device deficiencies, if any.
- Visit 5 (Office/Remote): Follow up visit [Visit 3+28 days (Window ± 5 days)]
 - Ensure CareLink upload was done
 - Collection of sensor site location
 - Review Pump therapy/adjust settings (see **Table 6**).
 - Retrain subject on 780G system as needed.
 - \circ $\;$ Review adverse events or device deficiencies, if any.

• Visit 6 (Office/Remote): Follow up visit [Visit 3+56 days (Window ± 5 days)]

- Ensure CareLink upload was done
- Collection of sensor site location
- Review Pump therapy/adjust settings (see **Table 6**).
- Retrain subject on 780G system as needed.
- Review adverse events or device deficiencies, if any.

Visit 7 (Office/Remote): End of Period 1 [Visit 3 + 84 days (Window ± 5 days)]

- Perform blood sample collection for HbA1c at Local Lab.
- $\circ \quad \text{Ensure CareLink upload was done} \\$
- \circ Collection of sensor site location
- Review Pump therapy/adjust settings (see **Table 6**).
- Retrain subject on 780G system as needed
- Measure/Collect height and weight.

CIP342 Clinical Investigation Plan Image: Comparison of the second s

- Collection of questionnaires
- Review adverse events or device deficiencies, if any.

For subjects randomized in Sequence A:

- Stop Auto Mode and start using Pump therapy in Manual Mode with SBL set at 65 mg/dL (3.6 mmol/L).
- Re-train the subject and parent(s)/guardian(s) on the use of pump therapy in Manual Mode as needed
- Visit 8 (Office/Remote): Start of Period 2 [Visit 7 + 14 days (Window + 3 days max)]
 - Ensure CareLink upload was done
 - Collection of sensor site location
 - Review Pump therapy/adjust settings (see **Table 6**).
 - Retrain subject on 780G system therapy as needed.
 - Review adverse events or device deficiencies, if any.

For subjects subject randomized in Sequence B:

- Train the subject and parent(s)/guardian(s) on the use of pump therapy in Auto Mode
- To start Pump therapy in Auto Mode.

Sequence B Only:

- Visit 8A (Office/Remote): Follow up visit [Visit 7 + 28 days (Window ± 5 days)]
 - Ensure CareLink upload was done
 - Collection of sensor site location

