 - Perform blood sample collection for creatinine clearance at local lab. If creatinine clearance test was performed ≤ 6 months prior to screening, only confirm date of collection at local lab and creatinine clearance value in medical chart. Note: Creatinine clearance threshold for exclusion< 30 mL/min and must be calculated with the Cockcroft, CKD-EPI or MDRD equations. The sites will follow routine practice for evaluation of the creatinine clearance.
 - $_{\odot}$ $\,$ Perform blood sample collection for HbA1c at the Local Lab.
 - \circ $\,$ Collect number of DKA in the last 3 months.

Run-In Phase 2:

Visit 2A* (Office/Remote): Start Manual Mode + SBL [Visit 1A + 0-3 days (Window + 5 days)]

Note: Visit 2A and Visit 1A can be combined to start Pump Therapy in Manual Mode + SBL.

CIP342 Clinical Investigation Plan Medtronic D00674412 Version E Page 43 of 96

- Train subject and parent(s)/guardian(s) on the MiniMed 780G system
- Train the subject and parent(s)/guardian(s) on the use of pump therapy in Manual Mode + SBL set at 65 mg/dL (3.6 mmol/L)
- Set-up subject CareLink Account.
- CareLink Training
- Start pump therapy in Manual Mode + SBL
- Collection of sensor site location
- Collection of questionnaires
- Review adverse events or device deficiencies, if any.
- Visit 3A (Office/Remote): Follow-up & Auto Mode start [Visit 2A + 7 days (Window +/- 5 days)]
 - Switch to Auto Mode
 - Ensure CareLink upload was done
 - Review Pump therapy/adjust settings (see **Table 6**)
 - Retrain subject on 780G system as needed
 - Collection of sensor site location
 - Review adverse events or device deficiencies, if any

Schedule of Events for subjects enrolling for the entire study duration as well as for the Continuation phase only:

- Period 1
 - Visit 12 (Office/Remote): Follow up visit [Visit 11/1A + 42 days (Window ± 5 days)]
 - Ensure CareLink upload was done
 - Collection of sensor site location
 - Review Pump therapy/adjust settings (see **Table 6**).
 - Retrain subject on 780G system as needed
 - Review adverse events or device deficiencies, if any
 - Visit 13 (Office): Follow up visit [Visit 11/1A + 126 days (Window ± 42 days)]
 - Ensure subject's reconsent from legal/guardian on protocol C or subsequent version was obtained before Visit 13 procedures are performed (if applicable)
 - Ensure CareLink upload was done
 - Collection of sensor site location
 - Review Pump therapy/adjust settings (see Table 6).
 - Retrain subject on 780G system as needed

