 - Review adverse events or device deficiencies, if any
 - Collection of questionnaires
 - Perform blood sample collection for HbA1c (Central Lab)
 - Randomize to one of the 2 arms:
 - Arm A2: Start pump therapy with MiniMed 780G BLE 2.0 system and DS5 Sensor in Auto Mode (treatment 2)
 - Arm B2: Continue pump therapy in Auto Mode (Treatment)

D00674412

For subjects randomized in Arm A2:

• Train subject on MiniMed 780G BLE 2.0 system and DS5 sensor

• Period 2

- Visit 14 (Office/Remote): Follow up visit [Visit 13+ 42 days (Window ± 5 days)]
 - Ensure CareLink upload was done
 - Collection of sensor site location
 - Review Pump therapy/adjust settings (see **Table 6**).
 - Retrain subject on MiniMed 780G system/MiniMed 780G BLE 2.0 system with DS5 sensor as needed
 - Review adverse events or device deficiencies, if any.
- Visit 15 (Office): End of Continuation Phase [Visit 13 + 84 days (Window ± 5 days)]
 - Perform blood sample collection for HbA1c (Central Lab)
 - $\circ \quad \text{Ensure CareLink upload was done} \\$
 - \circ Collection of sensor site location
 - Measure/Collect height and weight.
 - Return of devices
 - Collection of questionnaires
 - Review adverse events or device deficiencies, if any.

CIP342 Clinical Ir	vestigation Plan			
D00674412	Version E	Page 45 of 96	Medtronic	

Table 5. Visit Details and Data Collection

Visit	1	2	3	3A	4	5	6	7	8	8A	9	10	11	1A	2A	3A	12	13	14	15
Visit Name	Consent & Screening	Start Manual Mode	End of Run-in & Randomization	Auto Mode Start	Follow- up	Follow- up	Follow- up	End of Period 1	Start of Period 2	Auto Mode Start	Follow- up	Follow- up	End of Study Phase	Consent & Screening	Start Manual Mode + SBL	Follow up & Auto Mode start	Start Continuation Phase - Period 1	End of Continuation phase Period 1 & randomization	Start of Period 2	End of continuation phase period 2 - End of Study
Visit Type	Office	O/R	O/R	O/R	O/R	O/R	O/R	Office	O/R	O/R	O/R	O/R	Office	Office	O/R	O/R	O/R	0	O/R	Office
Target date	-	V1 + 0-3d	V2 + 14d	V3 + 0-3d	V3 + 14d	V3 + 28d	V3 + 56d	V3 + 84d	V7 + 14d	V7 + 28d	V7 + 42d	V7 + 70d	V7 + 98d		V1a + 0-3d	V2 + 7d	V11/1A + 42d	V11/1A + 126d	V13 + 42d	V13 +84d
Window	-	+ 5d	+ 14d	+ 2d	± 5d	± 5d	± 5d	± 5d	+3d	± 5d	± 5d	± 5d	± 5d		+ 5d	± 5d	± 5d	± 42d	± 5d	± 5d
Informed consent	х													As needed						
Eligibility criteria	х													х			X ²			
Review of Randomization Criteria			х															Х		
Randomization			Х															Х		
Demographics	х													Х						

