9.5.3 HbA1c

HbA1c is collected at Visit 1, Visit 7, Visit 11, Visit 13 and Visit 15; if subjects have completed run-in phase and are in the study phase and exit early, a HbA1c will be collected as described in Early Termination Visit. HbA1c will be collected at the Local Lab for Visit 1, Visit 7, Visit 11. HbA1c will be collected at the Central Lab for Visit 13 and 15.

All HbA1c blood specimens from the Continuation phase will be sent to and tested by a National Glycohemoglobin Standardization Program (NGSP) certified Central Laboratory. The blood sample will be destroyed according to the Central laboratory procedure after analysis.

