#### 7.9.2 Analysis of primary endpoint – continuation phase - betweentreatment difference in HbA1C – non inferiority test

The goal is to assess the non-inferiority in the mean Hba1c during the 12-week continuation phase period 2 in the Treatment MiniMed 780G BLE 2.0 system with the DS5 sensor in Auto Mode compared to Control MiniMed 780G System in Auto Mode. The between-treatment difference will be compared using the following hypotheses:

$$\begin{array}{l} H_0: \Delta HbA1c \geq 0.4\% \\ H_\alpha: \Delta HbA1c < 0.4\%. \end{array}$$

Where  $\Delta HbA1c$  is the difference of the average of HbA1c for Treatment MiniMed 780G BLE 2.0 system with the DS5 sensor in Auto Mode vs Control MiniMed 780G in Auto Mode at the end of the 12-week continuation phase period 2, will be assessed by using of mixed model adjusting by baseline value. It will be tested at the 0.025 (one-sided) significance level.

The 97.5% upper confidence limit of between-treatment difference will be calculated. If it is lower than 0.4%, the non-inferiority will be concluded.

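### SAP 7.4's ±14-day per-protocol rule for HbA1c voids Visit 13 values that the protocol's own ±42-day window allows

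*SAP*

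**What the plan says.** SAP 7.4 gives one timing rule for HbA1c in the PP analysis: "For per protocol analysis, if A1c is collected out of window (± 14 days from target visit date) A1c will be considered missing". It applies visit by visit and exempts none.

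The protocol's windows for HbA1c visits are not uniform. In the schedule of events (9.1), Visit 13 is "Visit 13 (Office): Follow up visit [Visit 11/1A + 126 days (Window ± 42 days". Section 5 describes the same flexibility: children "will use MiniMed 780G system in Auto Mode for 18 weeks +/- 6 weeks" before the second randomisation. The outcome visits are tight. Visit 7 is "End of Period 1 [Visit 3 + 84 days (Window ± 5 days", Visit 11 also has ±5 days, and Visit 15 is "End of Continuation Phase [Visit 13 + 84 days (Window ± 5 days".

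On the laboratory, protocol 9.5.3 says "HbA1c will be collected at the Central Lab for Visit 13 and 15". Visits 1, 7 and 11 use local labs, and so does Visit 1A in the schedule.

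The continuation primary endpoint is HbA1c at the end of period 2, which is Visit 15. SAP 7.9.2 says the difference "will be assessed by using of mixed model adjusting by baseline value" and does not name the visit that supplies the baseline. SAP 7.1.3 describes the PP analyses as done for sensitivity purposes.

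**The concern.** The SAP tolerance is wider than the protocol window at Visits 7, 11 and 15, so it does no harm there. At Visit 13 it is a third of the protocol window. A site can hold Visit 13 exactly as the protocol permits and have the HbA1c discarded as out of window. That is the reverse of what a per-protocol rule is for.

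Visit 13 is the randomisation visit for the continuation phase, and its HbA1c is the only scheduled pre-randomisation value from the central lab that also measures the endpoint. Visit 11 is a poor substitute, because Sequence A children reach it after 12 weeks in Manual Mode. Visit 13 is therefore the likely baseline covariate. If so, voiding it can remove a compliant child from the adjusted PP analysis. For a non-inferiority claim, readers compare PP with ITT. A PP estimate made imprecise by a date rule could appear to disagree with ITT for no clinical reason.

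**Working it through.** **1. The plan's own count.** The protocol expects about 80 randomised, 72 completing the study phase and 64 completing the continuation phase, with 10% drop-out per phase (14.6.1). 80 × 0.90 = 72.0 and 72 × 0.90 = 64.8, so the 64 is reproduced. It serves below as the base. The PP set could be smaller for other reasons.

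**2. The conflict by visit.**

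| HbA1c visit | Protocol window | SAP PP tolerance | Compliant values voided? |
|---|---|---|---|
| 7, 11, 15 | ±5 days | ±14 days | No |
| 13 | ±42 days | ±14 days | Yes, at 15 to 42 days from target |

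Permitted Visit 13 days: 2 × 42 + 1 = 85. Days within ±14: 2 × 14 + 1 = 29. Days permitted but voided: 85 − 29 = 56, or 56/85 = 65.9%.

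Visit 15 is timed from Visit 13, so an early or late Visit 13 does not put the outcome out of window.

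**3. Share of compliant Visit 13 values voided.** This depends on the spread of visit dates, which the documents do not give. For dates normal around target with SD σ, truncated to ±42 days, the share is 1 − [2Φ(14/σ) − 1] / [2Φ(42/σ) − 1]. At σ = 14 this is 1 − 0.6827/0.9973 = 0.315.

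| Assumed Visit 13 dates | Share voided | Of 64 |
|---|---|---|
| Normal, SD 5 days | 0.5% | 0.3 |
| Normal, SD 7 days | 4.6% | 3 |
| Normal, SD 10 days | 16% | 10 |
| Normal, SD 14 days | 32% | 20 |
| Triangular, (1 − 14/42)² | 44% | 28 |
| Normal, SD 20 days | 47% | 30 |
| Uniform, 56/85 | 66% | 42 |
| Centred 21 days off target, SD 14 to 7 days | 68% to 84% | 43 to 54 |

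Off-centre dates are not far-fetched. Protocol 9.1 also describes Visits 12 to 15 as running every 6 weeks. With Visit 12 at day 42, that would put Visit 13 near day 84, which is 42 days before target: inside the protocol window and outside the SAP tolerance.

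**4. Illustration of the cost if each voided value removes the child.** Inputs: margin 0.4%, one-sided 0.025, 1:1 allocation, true difference 0, n per arm. The HbA1c SD is an assumption, because the public text gives no figure. Power = Φ(0.4 / (SD × √(2/n)) − 1.96). With n = 32 and SD 0.5, the SE is 0.125 and power = Φ(3.20 − 1.96) = 0.89.

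| Children kept | Power, SD 0.5 | Power, SD 0.8 |
|---|---|---|
| 64 (none lost) | 89% | 52% |
| 54 (dates SD 10) | 84% | 45% |
| 44 (dates SD 14) | 75% | 38% |
| 22 (uniform) | 46% | 21% |

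These figures are unadjusted; baseline adjustment would raise them.

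**5. After the fix.** If Visit 13 is judged against its own window, 0 of 64 on-schedule values are voided.

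**The case against.** The strongest reply is that the rule voids a value, not a child. A missing HbA1c is not among the PP exclusions in SAP 7.1.3, and the Visit 15 outcome stays. A child drops out only if the baseline is Visit 13 and the model uses complete cases on that covariate, and the documents state neither. SAP 7.4 describes the primary analyses as using available data, and a model with Visit 13 as a repeated response would keep the child. A baseline definition may also sit in text removed from the public SAP. All of this stands, and it is why the loss is stated conditionally. In the other direction, a model that uses available outcomes does not by itself rescue a record with a missing fixed covariate, and protocol 14.4 rules out imputation.

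A reader might infer that the continuation PP analysis will lose many children. The documents do not support that. With tightly scheduled visits the loss is negligible, and nothing says how visits will spread.

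A reader might also infer that trial success is at risk, because protocol 14.5.1 requires both ITT and PP. That criterion is written under the study-phase primary endpoint, which is time in range and not HbA1c. The SAP's stated criterion (under 7.9.1) uses ITT alone.

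Finally, the Visit 13 date is fixed before the arm is assigned, so this deletion alone should fall evenly on the two arms. The cost is precision rather than bias.

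**Conclusion.** The conflict between the two windows is definite: on 56 of 85 permitted days, a compliant Visit 13 HbA1c is voided for PP. Its effect on the analysis is conditional. If Visit 13 is the model baseline and missing covariates are dropped, the share of children lost runs from under 1% to over 80%, depending on visit timing that the documents do not give. The power figures are illustrative, because the HbA1c SD is assumed. Only the continuation-phase PP sensitivity analysis is exposed; ITT and As Treated are not.

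One further reading should be closed off. If the Visit 15 target were counted from the target date of Visit 13 rather than its actual date, outcome values would be caught too. The protocol times Visit 15 from Visit 13 itself, so the documents do not support that reading, but SAP 7.4 does not say so.

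**What to change.** In SAP 7.4, limit the ±14-day PP rule to the outcome HbA1c values at Visits 7, 11 and 15. State that the Visit 15 target is counted from the actual Visit 13 date, and that a Visit 13 HbA1c is kept whenever it was drawn within its protocol window.

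In SAP 7.9.2, name Visit 13 as the baseline HbA1c, or state which visit is used, and say how a missing baseline is handled. If the sponsor intends another baseline, naming it removes most of the practical consequence.

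The cost is a few sentences in the SAP. Visit schedules, data collection and the ITT analysis do not change. The edit should be made before the continuation-phase data are analysed, so that the choice cannot depend on results.

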#### 7.5 Adjustments for Multiple Comparisons

Study endpoints will be tested with the use of a hierarchical gatekeeping procedure to control the type I error. The primary endpoints will be tested first and, if passing the significance testing, other endpoints will be tested in order.

CIP342 LENNY Statistical Analysis Plan	Form
Revision 2.0 Page 17 of 31	Medtronic

If a non-significant result (hypothesis not rejected) is encountered, formal statistical hypothesis testing will be terminated, and analysis of any subsequent endpoints (lower in hierarchy) will be considered as exploratory.

#### 7.5.1 Sequential testing for Study Phase

Fixed sequential testing of primary and selected secondary endpoints:

Study Phase Primary endpoint:

1. Between-treatment difference in percentage of time spent within range 70 - 180 mg/dL.

It will be tested for non-inferiority with a margin of 7.5%, as described in section 7.9.1 and a p-value < 0.05 will be considered statistically significant. If p-value < 0.05, continue to next test, else stop.

Study Phase Secondary endpoints:

- Between-treatment difference in Mean HbA1c at the end of each 12-week period.
   It will be tested for non-inferiority with a margin of 0.4%, if p-value < 0.05 reject null hypothesis and continue, else stop

- Between-treatment difference in percentage of time spent within range 70 180 mg/dL.
   It will be tested for superiority, if p-value<0.05 reject null hypothesis and continue, else stop

- Between-treatment difference in Mean HbA1c at the end of each 12-week period.
   It will be tested for superiority, if p-value<0.05 reject null hypothesis and continue, else stop

#### **7.5.2 Sequential testing for Continuation Phase**

Continuation Phase Primary endpoint:

1. Between-treatment difference in Mean HbA1c at the end of the continuation phase period 2.

It will be tested for non-inferiority with a margin of 0.4%, as described in section 7.9.2 and a p-value < 0.05 will be considered statistically significant. If p-value < 0.05, continue to next test, else stop.

Continuation Phase Secondary endpoints:

- Between-treatment difference in Mean HbA1c at the end of the continuation phase period 2.
   It will be tested for superiority, if p-value<0.05 reject null hypothesis and continue, else stop

- 3. Between-treatment difference in percentage of time spent within range 70 180 mg/dL during the continuation phase period 2.

It will be tested for non-inferiority with a margin of 7.5%, if p-value < 0.05 reject null hypothesis and continue, else stop

CIP342 LENNY Statistical Ana	lysis Pla	an	Form
Revision	2.0	Page 18 of 31	Medtronic

4. Between-treatment difference in percentage of time spent within range 70 - 180 mg/dL during the continuation phase period 2.

It will be tested for superiority, if p-value<0.05 reject null hypothesis and continue, else stop

Exploratory endpoints:

Analyses on secondary exploratory endpoints may be performed, and p-values could be reported but may not be claimed.

Safety endpoints:

No statistical test will be performed on safety endpoints.

